Study Protocol

1. Protocol Title

Sleep Management And Recovery after Trauma in Kids (SMART-Kids): Melatonin Pilot Trial

NCT04932096

IND reference number 157247

PI: [name], MCR

[name]

Oregon Health & Science University

Department of Pediatrics, Division of Pediatric Critical Care

[name]

[contact]

2. Objectives

This is a randomized controlled phase II intervention trial evaluating early melatonin and a sleep educational intervention versus placebo following pediatric traumatic brain injury (TBI). No changes to typical TBI care will be made. This single center trial will focus on feasibility and acceptability outcomes of a real world pragmatic sleep intervention frequently utilized in the outpatient setting among pediatric TBI patients when employed earlier in the recovery process during hospitalization. We will also obtain data on effectiveness to reduce sleep disturbances at 30-day outcomes assessment to help inform a larger trial that would be powered to evaluate effectiveness among a heterogeneous population.

3. Background

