study will primarily evaluate feasibility and acceptability of a real-world sleep intervention frequently employed in the pediatric TBI population within the outpatient setting. We will also explore whether earlier inpatient employment of standard SWD interventions (melatonin and sleep education) commonly administered in the outpatient setting can provide benefit when employed earlier in the disease course as an adjuvant to clinical TBI care.

4. Study Design

This is a pilot randomized controlled phase II intervention trial evaluating early melatonin and sleep education via handouts versus placebo following pediatric traumatic brain injury (TBI) in two parallel study arms. This single center trial will focus on feasibility and acceptability outcomes, but will also obtain data on clinical effectiveness to reduce sleep wake disturbances at 30-day outcomes assessment. Sleep disturbances (with questionnaires and actigraphy data from Fitbits), feasibility (with clinical data collection, participant survey), and acceptability (survey, medical chart review) outcomes will be collected.

The intervention of this study uses a dietary supplement (melatonin) and an educational intervention administered via handouts. This study is not designed to evaluate melatonin's therapeutic efficacy or potential to diagnose, cure, mitigate, or otherwise treat a specific medical disorder, only to evaluate potential benefits to the bodily function of sleep when used with sleep education. The combined intervention of melatonin and sleep education was designed to mirror real world clinical care employed in this population within the outpatient setting in order to be generalizable to a heterogeneous population that is representative of the pediatric TBI population; therefore, our trial is designed to be pragmatic and will be exploring effectiveness outcomes for SWD relevant to this population, rather than efficacy of any one part of the intervention. A primary focus will be feasibility and acceptability (including intervention usage) to inform a larger longitudinal trial that would be needed to account for unavoidable population heterogeneity in clinical characteristics and adherence to intervention recommendations within the clinical setting.

5. Study Population

a. Number of Subjects

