We expect to enroll between 30-50 patients based on eligibility over 2.5 years of recruitment. This estimate is based on the most recent hospital admissions data since the start of the COVID-19 pandemic estimating approximately 100 patients will qualify for the study over 2.5 years. Participants will be randomized 1:1 to receive the intervention. Recruitment and retention will be assessed during the trial as outcomes.

b. Inclusion and Exclusion Criteria

Children \geq 6 years and <19 years of age admitted with TBI (defined as injury to the head from external forces with severity mild, moderate, or severe classified by Glasgow Coma Scale) will be included.

Children under the age of 6 years will be excluded due to increased variability in baseline sleep patterns, daytime napping, and lack of standardized tools identifying sleep outcomes between children younger and older than 6 years. Patients over age 18 years will be excluded as they are primarily treated in adult care units and the study focus is pediatric. Patients unable to tolerate enteral medications within 72 hours of hospital admission, as defined by the clinical care Attending Physician, will be excluded from the study. Patients undergoing dialysis, requiring extracorporeal life support, or with significant liver dysfunction (defined as aspartate aminotransferase (AST) or alanine aminotransferase (ALT) more than 2 times the upper limit of normal for age) will be excluded. Patients about whom the Attending Physician has any safety

concerns regarding use of melatonin as per clinical judgement will be excluded from the study. Patients with abusive trauma will be excluded. Suspected or known prisoners are excluded. Pregnant patients are excluded. There will be no requirement for contraception during the trial in female patients of child-bearing age. Patients must have a parent or guardian with whom they reside in order to participate in the study given the parent-reported measures used for outcomes.

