Randomization: Patients will be randomized 1:1 to intervention and control arms using a covariate adaptive design through the randomize.net website. Given heterogeneity in age and TBI severity, we aim to balance these patient characteristics across the arms with a relatively small sample size. A covariate-adaptive design will achieve better balance than one based on block stratification, as such a scheme will increase a subject’s probability of being assigned to the arm that improves overall balance in age and TBI severity (Glasgow Coma Scale Score groups: mild 13-15, moderate 9-12, severe ≤ 8). Initially, we will assign patients 1:1 to each arm by simple randomization, until six patients have been enrolled in each arm; this will allow us to collect sufficient information on covariates and determine the distribution of age and TBI severity in each arm. Once this criterion has been met, the Pocock-Simon minimization algorithm will be implemented and subsequent patients will be randomized with a probability of 0.85 to the arm that lowers overall imbalance in age and TBI severity. All patients will be randomized within 72 hours of hospital admission.

Intervention: All patients will receive standard clinical care for TBI regardless of study arm. Patients randomized to the intervention will receive a bundled sleep intervention consisting of melatonin and sleep education via a handout provided in discharge paperwork. Melatonin doses of 3mg and 5mg will be administered as part of the intervention arm in standard doses based on patient weight to target approximately 0.1mg/kg and not to exceed 0.2mg/kg. Melatonin will be administered on the first night following consent, 1 hour prior to habitual bedtime, and continued nightly for 30-days. Each participant will start the melatonin or placebo intervention within 96 hours of hospital admission, varying with time of admission and consent. Patients randomized to receive the intervention will be given a written sleep education handout developed with age-based recommendations from the American Academy of Sleep Medicine and access to web-based sleep educational resources developed from similar materials used in the care of pediatric brain injury patients within the outpatient setting.

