The handouts delivered with discharge paperwork will be incorporated into the discharge instructions section within the electronic medical record by a research assistant. Handouts contain resources outlined below educating patients and families on the importance of sleep, sleep hygiene, sleep

routines, environmental changes to facilitate sleep, and relaxation techniques; the handouts were adapted from standard care provided in our outpatient program for TBI management (see details below). Further, a study in a pediatric ICU cohort designed to directly compare modes of educational intervention delivery, and included parents of pediatric TBI patients, recently showed an educational handout was just as effective as a scripted conversation or a short video when attempting to educate families about morbidities after hospital discharge, but the handout was the most sustainable and supported by hospital staff.[86]

Participants randomized to the control arm will receive placebo (microcrystalline cellulose) and the sleep education handout delivered with discharge paperwork as above. All patients will receive clinical care as usual for management of TBI. All traumatic brain injury patients at OHSU receive referrals for clinical follow up with the Pediatric Critical Care and Neurotrauma Recovery Program (PCCNRP); other referrals made to outpatient programs are made on an as needed basis depending on type of TBI and other concurrent injuries or morbidities identified during hospitalization. While in the hospital, current standard of care treats morbidities after TBI as needed and varies by clinical provider; there is no standard for treating sleep problems in the hospital. As outpatients, all hospitalized pediatric trauma patients at OHSU are referred to the PCCNRP clinic 4-6weeks after discharge. At this outpatient visit, a comprehensive assessment in physical function and morbidity is made by [name] (Pediatric Intensivist), which includes assessment of sleep; a brief neuropsychological assessment of cognitive function and a comprehensive psychological assessment are made by [name] (Pediatric Neuropsychologist). Given this study's intervention is designed for 30days and we plan to make no changes to clinical care, all patients in the trial will still have access to these evaluations at clinic appointments 4-6weeks after discharge.

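### With the handout in both arms, the effectiveness contrast is melatonin versus placebo, not the melatonin-plus-education bundle that Sections 2 and 4 describe

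*Combined protocol and SAP*

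**What the plan says.** All references are to the combined protocol and SAP.

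- Section 2 (Objectives) describes a trial "evaluating early melatonin and a sleep educational intervention versus placebo following pediatric traumatic brain injury (TBI").
- Section 4 (Study Design) repeats this: "evaluating early melatonin and sleep education via handouts versus placebo following pediatric traumatic brain injury (TBI) in two parallel study arms". It adds that the trial "will be exploring effectiveness outcomes for SWD relevant to this population, rather than efficacy of any one part of the intervention". It also says the study is meant "only to evaluate potential benefits to the bodily function of sleep when used with sleep education".
- Section 6 (Intervention) describes the active arm: "Patients randomized to the intervention will receive a bundled sleep intervention consisting of melatonin and sleep education via a handout provided in discharge paperwork". Access to web-based education is also listed there for that arm.
- Section 6 then describes the control arm: "Participants randomized to the control arm will receive placebo (microcrystalline cellulose) and the sleep education handout delivered with discharge paperwork as above".
- Later in Section 6, a research assistant places the handout after being told that a participant has enrolled. No arm condition is given, and participants are blinded.
- Table 1 stars SDSC total score as a primary outcome, under the heading for exploratory effectiveness outcomes. Section 8 compares it between arms by linear regression and describes this as examining the effectiveness of the trial's intervention. Section 8 also carries the secondary sleep-phenotype results forward as effect sizes for later trials.

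**The concern.** Sections 2 and 4 name education only on the active side of the comparison, and Section 6 defines the intervention as a bundle of melatonin and education. A reader of Section 8 would therefore take the between-arm SDSC difference as the effect of that bundle. The Section 6 control arm also receives the handout, so the randomized difference isolates the melatonin component. That sits badly with the Section 4 statement that no single component is the target.

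What is at stake is the label on the result. If the SDSC estimate, or the secondary estimates carried into later planning, is presented as the effect of melatonin plus education, it claims something this design does not measure. A later trial of the bundle against care without education would then be planned on a different contrast from the one estimated here. More participants would not cure this, because it concerns which quantity is estimated and not how precisely.

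**Working it through.** The plan states no figure that depends on this point, so there is none to reproduce. The check sets the passages side by side and then works out which contrast each control condition allows.

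**Step 1. Who receives what**

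| Place | Active arm | Control arm |
|---|---|---|
| Section 2 | melatonin + education | placebo; education not mentioned |
| Section 4, opening | melatonin + education handout | placebo; education not mentioned |
| Section 6, active arm | melatonin + handout + web access | not described |
| Section 6, control arm | (as above) | placebo + the same handout |
| Section 6, handout placement | on enrolment, no arm condition | on enrolment, no arm condition |
| Section 11b | may benefit directly | may lack direct benefit; indirect benefit from attention to sleep |

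Only one row states the full content of the control arm, and it includes the handout. The placement procedure and participant blinding agree with it. The sentence that covers both arms at once contrasts the pills: "Each participant will start the melatonin or placebo intervention within 96 hours of hospital admission". No passage says that controls receive no education.

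**Step 2. What the arm coefficient estimates**

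Let μ be the mean with neither component, m the effect of melatonin without education, e the effect of education without melatonin, and i their interaction. The effect of the bundle against neither component is m + e + i.

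*Control arm as Section 6 specifies it:*
- Active mean: μ + m + e + i
- Control mean: μ + e
- Difference: m + i

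This is melatonin versus placebo with the handout in both arms. With only these two means, neither e nor m + e + i can be estimated. To recover m + e + i as a·(active) + b·(control), the m term needs a = 1, the e term needs a + b = 1, and the μ term needs a + b = 0. The last two cannot both hold.

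*Control arm with placebo only, as Sections 2 and 4 could be taken to imply:*
- Active mean: μ + m + e + i
- Control mean: μ
- Difference: m + e + i

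This is the bundle effect.

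*Gap between the two:* (m + e + i) − (m + i) = e.

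The regression is the same in both cases; only its meaning changes. The Section 6 contrast equals the bundle effect only if e = 0, meaning that education does nothing without melatonin. The documents give no value for e.

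**Step 3. How many participants the description covers**

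Section 5a: "We expect to enroll between 30-50 patients based on eligibility over 2.5 years of recruitment". Allocation is 1:1, so controls number 30/2 = 15 to 50/2 = 25.

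**Step 4. Which results are affected**

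- Affected: the SDSC total score regression and the secondary effectiveness comparisons, in interpretation only.
- Not affected: recruitment (consented over approached) and retention (completed over consented). Neither uses the between-arm contrast.

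**The case against.** The strongest reply is that there is no real contradiction. Section 6 is the only place that specifies the control arm, and it is explicit. Sections 2 and 4 are one-line summaries in which placebo can simply name the comparator pill. Arm-neutral handout placement and blinded participants fit a handout for everyone. Section 4 also frames the aim as sleep benefit when melatonin is used together with education, and placebo plus handout is a natural comparator for that. Education in both arms is a legitimate add-on design. Effectiveness is exploratory in any case.

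Much of this stands. It supports taking the Section 6 control arm as the operative one, and it confirms that the analyses are valid. It also limits the harm: a later trial with the same two arms would use the right contrast, and the sentence that carries effect sizes forward concerns the secondary sleep-phenotype outcomes, not SDSC total score.

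It does not remove the point. The better the case for Section 6, the clearer it is that the trial measures melatonin on top of education. The plan still says that no single part is the target, defines its intervention as the bundle, and labels the between-arm difference as that intervention's effectiveness. Exploratory status and low power do not correct a label.

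A reader might go further in three ways that the documents do not support:

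- *The control-arm sentence in Section 6 is a drafting error and controls get placebo only.* Nothing says so, and the placement and blinding arrangements point the other way.
- *Section 6 itself sets the bundle against placebo.* Its active-arm text lists what that arm receives and makes no comparison.
- *Education support is known to differ between arms.* Web access is named only under the active arm, and Section 7 links online-resource reminders to an intervention phase. That phrase may mean a period of time, so this is an open wording question and not evidence of imbalance.

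**Conclusion.** The point holds as a mismatch between the stated aim and the contrast that the specified arms deliver. Followed as written, the plan would label the SDSC and secondary effectiveness estimates as effects of a melatonin-plus-education intervention, when they estimate melatonin versus placebo with the handout in both arms. The bundle effect and the handout effect cannot be recovered from these two arms.

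The difference between the two contrasts is e, the effect of education without melatonin. Its size is unknown from the documents and none is claimed. The description covers about 15 to 25 controls.

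The conclusion assumes that controls receive what Section 6 specifies. It does not mean that the regressions are invalid or that the trial fails its main purpose. Section 8 acknowledges low power for effectiveness, and recruitment and retention are untouched. The wording should be corrected before results are reported or used for planning.

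**What to change.** Reconcile Sections 2, 4 and 6 to one control condition, and align the wording on placebo-arm benefit in Section 11b with it. If the Section 6 control arm is confirmed:

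1. Restate the arms throughout as melatonin plus handout versus placebo plus handout.
2. State in Section 8 that the SDSC and secondary effectiveness models estimate melatonin versus placebo with the handout given to both arms.
3. Do not present these estimates, or the effect sizes carried into future trials, as effects of the bundle or of the handout.
4. State whether the web access in Section 6 and the online-resource reminders in Section 7 are the same in both arms.

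The model, outcome and tests stay as they are. The cost is protocol wording and a narrower stated conclusion.

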Screening: Children with traumatic brain injury (TBI) will be screened for inclusion in the study by the Trauma Research Group (TRG) on admission to Oregon Health and Science University or Doernbecher Children's Hospital. Research coordinators with the TRG are available to screen all TBI admissions for inclusion into active research studies 24 hours per day. Screening activities will take place under a HIPAA waiver per the "Activities Preparatory to Research" policy at OHSU. Given the extensive experience and training of the TRG, we expect very few if any screen failures of TBI admissions, and this will be actively monitored throughout the study period.

Recruitment Procedures: Recruitment will be maximized by using consistent trained staff within the TRG that have extensive experience consenting subjects and surrogates for research, including critically injured children. The recruitment process will be overseen by [name], a Pediatric Critical Care physician, with expertise in caring for critically injured children. TRG staff

are trained and mindful of the critical nature of traumatic brain injury and will ensure the appropriate time and conditions for obtaining informed consent. Individual staff are monitored to ensure adherence to TRG standard operating procedures and study protocols.

The appropriate time to approach patients will be determined by study staff and clinical care staff, and consent will be obtained within 72 hours of Pediatric Intensive Care Unit admission to ensure starting the intervention as early as possible. Delaying consent for critically ill patients will not adversely affect the study outcomes, but will allow for acute stabilization of patients prior to consideration of study inclusion, ensure ability to administer enteral medications, and to allow for determination by the primary clinical care team of a patient's likelihood of survival. Consent procedures will be reviewed at least quarterly during TRG coordinator meetings to ensure ongoing consistency. The minimum goal set for recruitment is 50% of eligible patients.

Retention: All patients consenting for inclusion will have phone, address, email contact information collected at time of consent. Outcomes will be obtained at 1-month follow-up as described.

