Text messaging will be used for system generated reminder prompts such as "Please sync your device"; or if battery is low, "Please charge your battery" during the 1-month study period while participants wear the Fitbit. Text messaging functions require sharing of participant phone numbers with the Fitabase platform and Twilio, Inc.

Feasibility benchmarks will be assessed every 6 months during the trial. If feasibility benchmarks are not met, study procedures and the protocol will be reviewed using input from stakeholders and preliminary data to determine if changes are warranted.

Table 1. Outcomes Evaluation and Analysis for Melatonin Trial

Outcome (time collected)	Measurement or Assessment Tool	Analysis
Feasibility Outcomes		
*Recruitment (6-monthly feasibility reviews)	Number subjects consented/approached; goal >50%	Descriptive percent
*Retention (6-monthly feasibility reviews)	Quantitative Number completed/consented; Goal >90%	Descriptive percent
Screen failure (6-monthly feasibility reviews)	Number approached/eligible patients; expect <<5%; eligible patients will be derived from the OHSU Trauma Registry and compared to study logs	Descriptive percent
Reasons for Participation/ Non-participation (time of approach/consent)	Qualitative response to survey: "Please describe reasons you chose [not to or to] participate in this research study"; "Could the study team do something different in the future to increase chances you would participate in future studies?"	Thematic analysis
Reasons for drop-out (30-day)	Qualitative response to survey: "We would like to know how we can improve our study in the future. Please tell us your reasons for leaving the trial"; "How could the study team have assisted you better in completing the trial?"	Thematic analysis
Adherence (30-day)	Pill counts: adherent if \geq 75% prescribed pills are taken at the follow-up study visit; will be counted as unknown if pill count not available Sleep tracking usage: actigraphy data and sleep diaries will be compared to age based recommendations; actigraphy counted as	Descriptive percent; Chi-square to compare intervention arms Descriptive percent; Chi-square to compare intervention arms

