a. Sharing of Results with Subjects

Data from this clinical trial will not be shared directly with participants. The results of the clinical trial and de-identified data will be made in accordance with NIH regulations and clinicaltrials.gov.

b. Data and Specimen Banking

No specimens will be stored. Study records will be retained for the longest regulatory retention period. After that time, records will be destroyed in a confidential manner.

8. Data Analysis

See Table 1 for outline of data analysis planned for study outcomes. As this is a pilot intervention trial, the focus will be on feasibility and acceptability of the pragmatic intervention trial. We will also explore effectiveness outcomes, but recognized we will be underpowered for a definitive effectiveness trial within this heterogeneous population selected to be representative of the population of interest. We will use our pilot trial to inform a future larger trial that will include longitudinal real world health outcomes relevant to the pediatric TBI population if supported by our preliminary results.

Prior to evaluating outcomes, we will perform a thorough descriptive analysis of participant baseline characteristics (age, race, ethnicity, gender, pre-injury comorbidities, TBI characteristics including severity, location, and type). We will examine patterns of missingness in our outcomes collected at 1-month, differences in participant and non-participant characteristics, and differences in participants who completed versus dropped out of the study to ascertain potential bias. Additionally, we will describe and compare the distribution of patient and clinical characteristics, including age and TBI severity, across treatment groups to ensure our randomization protocol was successful. Comparisons between groups will be made using chi-square tests for categorical variables. Depending on characteristics of the data, t-tests and Mann-Whitney U tests will be used to compare continuous variables between groups. We plan to perform both intention to treat and per protocol analyses.

Quantitative feasibility outcomes will be presented as a percentage of patients, the denominators of which are listed in Table 1. Comparisons between groups will be made with chi-square tests.

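### Table 1 defines screen failure as the share of eligible children approached yet expects well under 5%, and the recruitment goal uses a different denominator in section 5e than in Table 1

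*Combined protocol and SAP*

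**What the plan says.** Two places set out the feasibility measures: Table 1 in section 6 and the recruitment text in section 5e.

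- **Screen failure, Table 1:** "Number approached/eligible patients; expect <<5" (per cent). On the denominator, the row adds that "eligible patients will be derived from the OHSU Trauma Registry and compared to study logs".
- **Screen failure, section 5e:** "we expect very few if any screen failures of TBI admissions".
- **Recruitment, Table 1 (starred as primary):** "Number subjects consented/approached; goal >50" (per cent).
- **Recruitment, section 5e:** "The minimum goal set for recruitment is 50% of eligible patients".
- **Expected numbers, section 5a:** "We expect to enroll between 30-50 patients based on eligibility over 2.5 years of recruitment", on an estimate that "approximately 100 patients will qualify for the study over 2.5 years".
- **Status of Table 1, section 8:** "Quantitative feasibility outcomes will be presented as a percentage of patients, the denominators of which are listed in Table 1".

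Section 6 has the feasibility benchmarks checked every 6 months. A missed benchmark leads to a review of procedures and protocol. Section 10 states that there are no prespecified stopping criteria.

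**The concern.** The screen-failure row is inverted. Its numerator counts children who were approached, so the more complete the screening, the higher the figure. Read literally, a team that approached every eligible child would report 100% where far less than 5% is expected, and a team that approached almost nobody would match the expectation. Section 8 makes the Table 1 denominators the reporting ones, so the row is a working definition. No other section corrects it.

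The recruitment goal is a separate inconsistency. Approached and eligible children are different counts, as Table 1 itself shows by forming a ratio of the two. A primary outcome therefore has two goals that can give different answers on the same data.

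Feasibility is the main purpose of this pilot and is meant to inform a larger trial, for which reach among eligible children is a key input. The two faults also interact: the recruitment goals separate when eligible children are missed, and the screen-failure row is the one meant to reveal that.

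**Working it through.** **Inputs.** Eligible children E = about 100 and enrolment 30 to 50 (section 5a). Screen-failure ratio and expectation, and recruitment goal on approached children (Table 1). Recruitment goal on eligible children (section 5e). I take the children who qualify in section 5a to be the eligible children of Table 1 and section 5e. A is the number approached.

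**Step 1: the screen-failure figure as written.** The ratio is A/E, expected far below 5%.

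- A/100 < 0.05 gives A ≤ 4.
- Every enrolled child must first be approached, so A ≥ 30 to 50 and A/E ≥ 30/100 to 50/100, that is 30% to 50%, even if every approached child consents.
- If half of those approached consent, A = 30/0.5 to 50/0.5 = 60 to 100, and the ratio is 60% to 100%.

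The expected value cannot be reproduced from the written formula. This does not hinge on the rounded 100: enrolling 30 with under 5% approached needs E > 30/0.05 = 600.

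**Step 2: the complement.** (E − A)/E < 0.05 with E = 100 gives A from 96 to 100. This agrees with the row label, with the section 5e expectation, and with comparing the registry against the study logs.

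**Step 3: the two recruitment goals.** Table 1 needs the smallest whole number c with c/A > 0.5, which is floor(A/2) + 1. Section 5e needs c/E ≥ 0.5, which for E = 100 is always 50.

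| Approached (of 100 eligible) | Consents needed, Table 1 | Consents needed, section 5e | Gap |
|---|---|---|---|
| 100 | 51 | 50 | 1 |
| 99 | 50 | 50 | 0 |
| 98 | 50 | 50 | 0 |
| 97 | 49 | 50 | 1 |
| 96 | 49 | 50 | 1 |
| 95 | 48 | 50 | 2 |
| 90 | 46 | 50 | 4 |

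The first five rows are those with fewer than 5% missed. The last two lie outside the plan's expectation.

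**Step 4: sensitivity to the approximate 100, with fewer than 5% missed.**

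- E = 90, A = 86 to 90: Table 1 needs 44 to 46, section 5e needs 45; gap at most one.
- E = 110, A = 105 to 110: Table 1 needs 53 to 56, section 5e needs 55; gap at most two.

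**Step 5: where the goals give different verdicts.** The planned 30 to 50 is 30% to 50% of about 100 eligible, so only the top value reaches the section 5e minimum. Lower in that range the Table 1 goal can still be met: 40 consents pass with 79 approached (40/79 = 50.6%), and 30 pass with 59 approached (30/59 = 50.8%). Against 100 eligible these are 40% and 30%, and both fail section 5e. They require 21% and 41% of eligible children to be missed, so they illustrate the mechanism and are not forecasts.

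**The case against.** The best defence is that the screen-failure row is a clerical slip whose intent is plain. It is not starred, it is analysed descriptively, and it states an expectation where the neighbouring rows state a goal, so it may not be a benchmark that triggers a review at all. A team seeing about 98% under that label would notice at once, and the same two counts give the complement. On recruitment, section 8 already settles the reporting denominator, a floor on eligible children and a target on approached children can both be pursued, and the gap is trivial if screening works as planned.

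Much of this stands, and it keeps the point small. It does not remove it. The slash cannot be read loosely: the recruitment and retention rows beside it use it as numerator over denominator, and section 8 relies on that. A defined outcome should not depend on readers spotting that it is upside down. Section 8 fixes which recruitment percentage is reported, but it neither withdraws nor aligns the section 5e goal.

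It is also fair to say that the complement is an inference, though a well-supported one, and that the documents do not show which recruitment goal the sponsor wishes to keep. The sponsor should confirm both.

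**Conclusion.** Both parts hold. The screen-failure formula is wrong as written: it allows at most 4 approaches among about 100 eligible children, against 30 to 50 planned enrolments. The recruitment outcome has two unreconciled goals. Their difference is at most one consent when fewer than 5% of about 100 eligible children are missed, and at most two across 90 to 110 eligible; it becomes material only if many are missed. The wording difference between exceeding 50% and reaching at least 50% matters only at exactly 50%.

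The consequence is limited. A missed benchmark prompts a review and nothing more, there are no stopping criteria, and no test, significance level, power or sample size depends on either figure. It is worth correcting, at the lower end of that category. The size of the recruitment gap depends on the approximate 100 being the eligible count; the inversion of the screen-failure row does not.

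**What to change.** - **Table 1, screen failure:** define it as (eligible − approached)/eligible, keeping the sponsor's expected value and the Trauma Registry denominator. The sponsor should confirm that this is what was meant.
- **Section 5e, recruitment:** use one denominator. Following section 8, the simplest choice is to align with Table 1, for example: the recruitment goal is more than 50% of approached patients (consented/approached). If the sponsor prefers the eligible-based goal, Table 1 should change instead.
- **Six-monthly reviews:** report the eligible, approached and consented counts, so that the share of eligible children enrolled stays visible whichever goal is kept.

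The cost is two one-line edits and three counts per review. No new data are needed, since section 5b already retains screening information and Table 1 already plans the registry comparison. Sample size and analysis are unchanged.
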